5.2. Primary endpoint

- Residual volume at 1st flow-stop i.e., post catheterisation volume minus volume at 1st flow-stop, both derived from a catheterisation profile, [mL]. (*Catheterisation by HCP*)

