5.4. Assessments

Assessments (Catheterisation performed by the HCP):

- Position of the subject when performing the catheterisation, [sitting/standing]
- Catheter used for catheterisation (Test Product/Comparator, including catheter size (CH12/CH14))
- Urine volume from 2nd until 10th flow stop (derived from catheterisation profile), [mL]
- Urine volume measured post catheterisation (derived from catheterisation profile), [mL]
- Is subject menstruating at visit (yes/no)

Backup assessments (recorded by the HCP to replace endpoints if needed, in case of damaged profile recordings and/or readouts):

- Urine volume at 1st flow stop (scale), [g].
- Urine volume measured post catheterisation (scale), [g]
- Urine volume pre-catheterisation measured with a bladder scanner (triplicate measurements), [mL]
- Time for start of catheterization ([HH+:nn],[hours and minutes]
- Number of flow-stop episodes counted by HCP, [number]

Haematuria assessed by dipstick:

- Dipstick specific gravity, post catheterisation
 - (1.000/1.005/1.010/1.015/1.020/1.025/1.030)
- Dipstick haematuria, post catheterisation, [7-point scale]
 - Non-haemolysed – 0 Ery/ul (NEGATIVE)
 - Non-haemolysed – 10 Ery/ul (+/) (NEGATIVE)
 - Non-haemolysed – 80 Ery/ul (2+) (POSITIVE)
 - Haemolysed – 10 Ery/ul (+-) (NEGATIVE)
 - Haemolysed – 25 Ery/ul (1+) (POSITIVE)
 - Haemolysed – 80 Ery/ul (2+) (POSITIVE)
 - Haemolysed – 200 Ery/ul (3+) (POSITIVE)
- Dipstick leukocyturia post catheterisation, [5-point scale]
 - 0 Leu/µL - Negative
 - 15 Leu/µL - (1+)
 - 70 Leu/µL - (2+)
 - 125 Leu/µL - (3+)
 - 500 Leu/µL - (4+)

Assessments on subgroup all enrolled subjects at DK sites (Self-catheterisation):

- Urine volume pre-catheterisation measured with a bladder scanner (triplicate measurements), [mL]
- Position of the subjects when performing the catheterisation, [sitting/standing]
- Catheter used for catheterisation (Test product/comparator, including size (CH12/CH14))

- Residual volume post catheterisation (PVR) measured with a bladder scanner (triplicate measurements) [mL]
- Discomfort at insertion measured using the visual analog scale (VAS) [cm]
- Discomfort at withdrawal measured using the VAS [cm]
- Discomfort during emptying of bladder measured using the VAS [cm]
- Discomfort at end of emptying the bladder measured using the VAS [cm]

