- Pre-catheterization volume measured in triplicate with a bladder scanner. All measurements must be above 150 ml to proceed

- Catheterisation with 1st randomly assigned product (by HCP)
 - **NB!** HCP should count to 3 sec. if suspicious of a flow-stop before rotating the catheter to make it more clear on the profile.
- Catheterization profile (urine volume + number of flow stops)
- Volume at 1st flow stop and post catheterization volume noted from scale
- Number of flow stops noted
- Catheter used for catheterization (including size), position, and time for start of catheterization is noted
- Residual volume (PVR) (bladder scanner) (three measurements)
- Post-catheterisation dipstick test for haematuria, leukocyturia and Specific gravity
- Scheduling Visit (V2), after Baseline Visit (V1) (within visit window)
- Complete eCRF

Visit 2 (V2):

NB! Ask for change in relevant medical history since last visit. The subject should not have changed their medication the last 24 hours before V2 or show symptoms of UTI (assessed by investigator). If signs of UTI, they must be rescheduled and registration of AE. The position used for the HCP catheterisation must be the same as the position at visit 1.

- Review of Adverse events/Serious adverse events/Adverse device events, Device deficiencies and Protocol Deviations
- Review of changes in concomitant medication
- Information regarding menstrual cycle
- Pre-catheterization volume measured in triplicate with a bladder scanner. All measurements must be above 150 ml to proceed
- Catheterisation with 2nd randomly assigned product (by HCP)
 - **NB!** HCP should count to 3 sec. if suspicious of a flow-stop before rotating the catheter to make it more clear on the profile.
- Catheterization profile (urine volume + number of flow stops)
- Volume at 1st flow stop and post catheterization volume noted from scale
- Number of flow stops noted
- Catheter used for catheterization (including size), position, and time for start of catheterization is noted
- Residual volume (PVR) (bladder scanner) (three measurements)
- Post-catheterisation dipstick test for haematuria, leukocyturia and Specific gravity.
- DK only: Subjects will be asked to perform an additional self-catheterization at site after fluid intake
 - Pre self-catheterization volume measured in triplicate with a bladder scanner. All three measurements must be above 150 ml to proceed.
 - Post self-catheterization measure residual volume with triplicate bladder scan.

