10.3. Analysis of the primary endpoints

Residual volume at first flow-stop, will be analysed in a linear mixed model (LMM) with subject included as a random component. Evidence of superior effect will be concluded, if the 95% confidence interval of the difference between comparator and investigational device, do not include zero.

The model will include following fixed effects.

- Visit (Visit 1 and 2 of catheterisation)
- Device (comparator and investigational device)

The primary endpoint will be evaluated with the null hypothesis being rejected at a 5% significance level (alpha 0.05).

Analysis of sensitivity

- The primary analysis will furthermore be analysed in the PP population, where subjects have received treatment as per protocol.

- Also, a Wilcoxon signed rank test will be applied the primary analysis, under the assumption of data not being normally distributed.

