10.1. Level of significance and power

A significance level of alpha 0.05 (2-sided) will be applied.

The power for concluding superiority of the investigational device is at least 90% or higher.

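### The primary RV1 model omits the pre-catheterisation bladder volume scanned at each visit, so some precision may be lost; the planned analysis remains valid and unbiased

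*Combined protocol and SAP*

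**What the plan says.** Section 5.2 defines the primary endpoint as "Residual volume at 1st flow-stop i.e., post catheterisation volume minus volume at 1st flow-stop, both derived from a catheterisation profile, [mL"]. Section 10.3 says that it "will be analysed in a linear mixed model (LMM) with subject included as a random component", and then gives a list ("The model will include following fixed effects") of two terms, visit and device. There are two sensitivity analyses: the per-protocol population, and a rank test ("Also, a Wilcoxon signed rank test will be applied the primary analysis, under the assumption of data not being normally distributed"). Neither adjusts for bladder volume.

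Section 7.2 lists the same step directly before the catheterisation by the health care professional at Visit 1 and at Visit 2: "Pre-catheterization volume measured in triplicate with a bladder scanner. All measurements must be above 150 ml to proceed". No upper limit is given. The flow-chart in 7.3 puts Visit 2 one to seven days after Visit 1. Section 5.4 files the scan ("Urine volume pre-catheterisation measured with a bladder scanner (triplicate measurements), [mL"]) among the backup assessments, for use when a profile recording is damaged. The scan thus serves as a check before proceeding and as a backup, and not as a covariate.

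**The concern.** RV1 is part of the urine in the bladder when the catheter goes in. Filling at each visit is controlled only by the 150 mL floor, so one subject may arrive with quite different volumes at the two visits.

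The random subject effect removes that subject's usual level, and the visit effect removes the average shift between visits. Neither removes the subject's own change in filling from one visit to the other. If RV1 depends on filling, that change adds noise to the device contrast.

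The scan is taken before the device is used at that visit, so the device cannot have altered the reading. It is a legitimate period-specific baseline. At stake is the width of the confidence interval on which the whole pass/fail decision rests.

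**Working it through.** **Inputs.** From 10.6: difference 15 mL, SD 50 mL (comparator) and 15 mL (active), no within-subject correlation, 60 subjects. From Level of significance and power: "A significance level of alpha 0.05 (2-sided) will be applied". The correlation r between the within-subject difference in RV1 and the within-subject difference in filling is not in the documents. It is an assumption here, shown as a range.

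**1. The plan's own figure.** The variance of the paired difference is 50² + 15² = 2725, so its SD is 52.2 mL. The noncentrality for 60 pairs is 15 / (52.2/√60) = 2.23. A two-sided paired t-test then has 59.1% power, not the 87.7% in Table 10-1. All four rows of the table (71.9, 81.2, 87.7 and 92.2%) are reproduced by 80, 100, 120 and 140 pairs, twice the listed numbers. That is a separate sample-size matter; here 59.1% is the base that the stated inputs give.

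**2. Effect of adjustment.** A covariate with correlation r multiplies the residual SD by √(1 − r²) and uses one more degree of freedom (58 becomes 57).

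| r | SD of difference, mL | Power, 60 pairs | 95% CI half-width, mL |
|---|---|---|---|
| unadjusted | 52.2 | 59.1% | 13.49 |
| 0.2 | 51.1 | 60.8% | 13.22 |
| 0.3 | 49.8 | 63.1% | 12.87 |
| 0.41 | 47.6 | 67.0% | 12.31 |

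If r = 0, power changes from 59.05% to 59.03%, about 0.03 points.

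**3. How large r can be.** Suppose one slope b applies to both devices. On the active device, filling cannot explain more than the whole variance, so b² × Var(filling) ≤ 15² = 225. With equal filling variance at both visits and fillings not negatively correlated between visits, the variance of the difference in RV1 that filling explains is at most 2 × 225 = 450. Hence r² ≤ 450/2725 = 0.165, and r ≤ 0.41.

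Reaching that limit requires filling to explain all of the variation on the active device. If filling correlates 0.5 with active-device RV1, then r² ≤ 450 × 0.25/2725 = 0.041, so r ≤ 0.20 and the gain is under 2 points.

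**4. Another base.** An SD of difference of 36.9 mL (within-subject correlation about 0.9) roughly matches the table at 60 pairs. From there, power goes from 87.2% unadjusted to 88.5% at r = 0.2 and 90.0% at r = 0.3. The limit in step 3 rests on the variance of 2725 and does not carry over to this base.

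**5. Bias.** In a simulation of the crossover differences at SD 36.9 mL, the mean estimated device effect was about 15 mL with and without the covariate, at r = 0.3 and at r = 0.5.

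**The case against.** The strongest reply is that nothing in 10.3 is wrong. Device, visit and random subject form a standard crossover analysis. Sequence is randomised (5.7), so filling is balanced between devices in expectation. The planning SDs are marginal and already contain variation in filling. All of this stands.

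The benefit is also undemonstrated. That RV1 cannot exceed bladder volume shows little, because planned means of 25 and 10 mL lie far below a 150 mL floor, and a ceiling does not imply a correlation. Section 5.5 describes suction as arising while the bladder wall collapses around the eyelets, with repositioning towards the end of drainage. A residual set that late need not follow the starting volume. This stands as a reason to expect a small r, though it does not show that r is zero.

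A reader might infer that r = 0.5 is plausible, and that adjustment is then worth 60/(1 − 0.25) = 80 subjects in place of 60. The plan's figures do not support that for a single common slope: on its stated variances r stops near 0.41. A larger r would need a steeper slope on the comparator, that is, a device-by-volume interaction.

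Finally, a raw visit-level volume in a random-subject model can blend the between-subject and within-subject slopes, whereas the power figures above concern the within-subject slope only. That objection is sound, and the fix allows for it.

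**Conclusion.** This is an inexpensive improvement to a valid analysis. The scan is collected before the catheter is used at both visits and is left out of the primary model and both sensitivity analyses. The omission can widen the confidence interval. It does not bias the device effect or inflate the type I error.

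On the plan's inputs the gain lies between nothing and about 8 points of power (59.1% to about 67%), and is probably a few points. The upper end assumes one common slope, equal filling variance, fillings not negatively correlated across visits, and no within-subject correlation in RV1. The cost if filling is irrelevant is one degree of freedom: negligible, but not nil.

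A reader might infer that adjustment would bring the trial to its stated power. It would not: even at the upper limit, 67% is far below the 87.7% in Table 10-1 and the 90% stated under Level of significance and power. That shortfall must be corrected on its own and adds no weight to this point.

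**What to change.** Before unblinding, amend 10.3 so that the primary linear mixed model includes the mean of the three pre-catheterisation scans at that visit as a continuous covariate. Enter it as two terms: the subject's mean across the two visits, and the visit's deviation from that mean. The second term carries the within-subject slope, which is the one that sharpens the device contrast. Report the unadjusted model as a sensitivity analysis.

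The cost is two terms in the SAS model and a sentence or two in 10.3. No new data are needed, because the scans are already required at both visits. Prespecification matters: section 5.8 keeps the statistician blinded until database lock, and a covariate added after that would be post hoc.

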10.4. Analysis of secondary endpoints

- Number of flow-stop episodes will be analysed, in a generalized liner mixed model (GLMM), with subject included as a random component. Evidence of effect will be concluded, if the lower 95% confidence limit of the risk ratio between comparator and investigational device, is more than 1.
- Average residual volume post catheterisation and discomfort will be presented with Descriptive statistics for a continuous variable (N, Mean, SD (standard deviation), Median, Min and Max.)

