3.1. Objective (s)

Primary objective: To demonstrate superiority of the new compact catheter in terms of improved bladder emptying, with the catheterization performed by a health care professional.

Secondary objective: Is to assess safety of the new compact catheter in support of the CE marking

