5.3. Secondary endpoints

- Number of flow-stop episodes derived from a catheterisation profile (catheterisation performed by a healthcare professional), [number].
- Average residual volume post catheterisation (PVR) measured with a bladder scanner (triplicate measurements), [mL],
- Number of Adverse events, [number]

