10.1. Statistical design, methods, and analytical procedures

The primary objective will be evaluated by analysing the primary endpoint, supported by the secondary endpoint of flow-stop, and the secondary objective will be evaluated by analysing the secondary endpoints of adverse events and discomfort.

Baseline assessments and endpoints will be reported by descriptive statistics and/or listed.

Summaries will be presented by device i.e., investigational and comparator device and if relevant, by other grouping variables i.e., HCP and self-catheterisation.

Descriptive statistics for continuous variables are presented with N, Mean, SD (standard deviation), Median, Min and Max, where N denotes the number of subjects contributing with non-missing data. For discrete variables, descriptive statistics are presented with N and percentage, where percentage is based on the total number of subjects/observations with non-missing data.

All statistical analysis will be performed with SAS (version 9.4/Enterprise Guide version 7.1).

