10.2. Pass/fail criteria

To demonstrate superiority of the investigational device, the null hypothesis of the primary endpoint must be rejected, at a 5% significance (alpha 0.05).

11. Data management

Data management and the final statistical analyses of all measurements described in this protocol are carried out by the Clinical Strategies team, Coloplast A/S.

Data will be collected through an electronic data capturing (EDC) system on electronic Case Report Form (eCRF), a secure, internet-based case report form. This system will be used to record all subject information collected in the investigation for secure data tracking and centralised data monitoring ("remote monitoring") done by monitors, as defined in the monitoring section.

The EDC system used is Rave EDC, version 2022.3.0, delivered by Medidata Solutions Inc. The system is designed to be compliant with the FDA requirements of 21 CFR part 11. It is a validated data management system allowing only qualified and trained personnel to enter the system. The system has full audit trail and electronic signature.

The data management system has restricted role-based access control. The principal investigator or delegate an CRA must be trained in the system prior to getting access. The sponsor will be responsible for training the principal investigator or delegate, in completion of the eCRF. The training is web-based and must be completed before access to the investigation is granted. Training will be documented in the data management system. The data manager will also demonstrate the system on a virtual meeting. Only the principal investigator, or delegate, will be authorised to enter data in the eCRF.

The monitor, using his/her personal login information shall verify all critical data points against the source documents and issue electronic queries for the authorised clinical site personnel to respond, as defined in the monitoring section.

A critical quality control will be performed by the sponsor's data management team and queries issued where needed. Such queries must be resolved by the site personnel.

The principal investigator, using his/her personal login information, shall sign each eCRF before the database can be locked. This must be done after approval from the data management team.

Automated, real-time access to the data enable control on study compliance and safety assessments.

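### Section 10.4 gives flow-stops a formal conclusion rule with no condition on the primary result, although flow-stops is meant only to support the primary endpoint

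*Combined protocol and SAP*

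**What the plan says.** The primary objective in section 3.1 is "To demonstrate superiority of the new compact catheter in terms of improved bladder emptying, with the catheterization performed by a health care professional". Section 10.1 (Statistical design, methods, and analytical procedures) says how it is to be judged: "The primary objective will be evaluated by analysing the primary endpoint, supported by the secondary endpoint of flow-stop".

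Two endpoints then receive a formal decision rule:

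- RV1, in section 10.3: "Evidence of superior effect will be concluded, if the 95% confidence interval of the difference between comparator and investigational device, do not include zero".
- Number of flow-stop episodes, in section 10.4: "Evidence of effect will be concluded, if the lower 95% confidence limit of the risk ratio", comparator to test device, is above 1.

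The other efficacy and discomfort measures in 10.4 are descriptive only. Section 10.5 lists or summarises adverse events.

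The general level is set under Level of significance and power: "A significance level of alpha 0.05 (2-sided) will be applied". The Pass/fail criteria section says: "To demonstrate superiority of the investigational device, the null hypothesis of the primary endpoint must be rejected, at a 5% significance (alpha 0.05". Neither section mentions flow-stops. No part of section 10 gives a testing order, an alpha split or a condition linking the flow-stop conclusion to RV1.

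**The concern.** A supporting endpoint needs a primary result to support. The rule in 10.4 works the same way whether RV1 succeeds or fails, and the plan does not say how a positive flow-stop result would be read after a missed primary.

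Flow-stops was singled out for a decision rule while the measures beside it were left descriptive. The natural reading is that its conclusion carries formal weight. If RV1 is missed, the report may still present a formal statement of effect on a measure that the plan ties to the bladder-emptying objective. Error control would then not cover the two formal statements together, and the status of the second would be argued after the data are seen.

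**Working it through.** The plan states no joint error rate for the two rules, so there is no figure of its own to reproduce. The check is of the rules as written.

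**Inputs from the plan**

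- Overall level 0.05, two-sided (Level of significance and power). In the direction favouring the test device this is 0.05 / 2 = 0.025.
- RV1 rule: the 95% interval for the difference excludes zero (10.3). A false conclusion in favour of the test device has probability 0.025.
- Flow-stop rule: the lower 95% limit of the comparator-to-test ratio is above 1 (10.4). This rule points one way only. If the limit comes from a two-sided 95% interval, as the general two-sided level implies, a false conclusion has probability 0.025.
- Condition on RV1 for flow-stops: none.

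**Assumption.** The documents give no correlation between the two test statistics. Both endpoints are derived from the same catheterisation profile (5.2 and 5.3), so positive correlation is plausible. A range is shown.

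**Step 1: no effect on either endpoint, independent tests**

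P(at least one false favourable conclusion) = 1 − (1 − 0.025)² = 1 − 0.975² = 0.0494.

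The part that comes from a flow-stop conclusion standing alone after a missed RV1 is 0.025 × 0.975 = 0.0244. Added to the 0.025 for RV1, this gives the same 0.0494.

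**Step 2: correlated tests**

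With bivariate normal test statistics and correlation ρ, the probability is 1 − Φ₂(1.96, 1.96; ρ).

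| Assumed ρ | At least one false favourable conclusion |
|---|---|
| 0 | 4.94% |
| 0.3 | 4.76% |
| 0.5 | 4.54% |
| 0.7 | 4.17% |
| 0.9 | 3.52% |
| RV1 alone, for comparison | 2.50% |

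Whatever the dependence, the probability cannot exceed 0.025 + 0.025 = 0.05.

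**Step 3: the same, with flow-stops tested only after RV1 succeeds**

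- If RV1 truly has no effect, any false conclusion first requires a false RV1 rejection: at most 0.025.
- If RV1 has a real effect and flow-stops has none, a false conclusion requires a false flow-stop rejection: at most 0.025.

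The joint rate in the favourable direction is therefore held at 2.5% in every case, with RV1 still tested at its full level.

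**Step 4: sensitivity to how the limit is built**

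If the lower limit in 10.4 were a one-sided 95% bound, the flow-stop rule alone would carry 0.05. The independent-case figure would be 1 − 0.975 × 0.95 = 0.0738. The two-sided statement in the plan argues against this reading, so it is not used for the conclusion.

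**The case against.** The strongest reply is that the plan already protects the claim that matters. The Pass/fail criteria require rejection on the primary endpoint. The hypothesis in section 3.2 names only residual volume at first flow-stop. Section 5.3 lists flow-stops as secondary, and section 10.1 gives it a supporting role. Even the wording differs: RV1 leads to a conclusion of superior effect, flow-stops only to a conclusion of effect. There is only one formal secondary test, and the plan makes no claim of family-wise control.

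Most of this stands, and it rules out three stronger readings that a reader might infer.

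- *That the bladder-emptying objective has two chances of success.* It does not. Under the Pass/fail criteria a flow-stop result cannot demonstrate superiority after RV1 fails, so the type I error of that decision is as stated.
- *That two tests at 5% give 1 − 0.95² = 9.75%.* That sum counts flow-stop conclusions against the test device, which the one-directional rule in 10.4 cannot produce.
- *That a chance of missing RV1, taken from the power calculation, shows how often a false flow-stop conclusion would follow.* Power in section 10.6 assumes a true 15 mL difference, whereas the error rates above assume no effect on either endpoint. A flow-stop conclusion after a missed but real RV1 effect is not thereby shown to be false.

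What the reply does not remove is the gap in 10.4. The Pass/fail criteria govern superiority. They neither withdraw the separate flow-stop conclusion nor make it descriptive when RV1 fails.

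**Conclusion.** The point holds as a gap in specification with a modest effect on error. Section 10.4 allows a formal flow-stop conclusion after a failed primary, which does not fit the supporting role given in 10.1. The superiority decision is not inflated.

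Across the two formal rules, the chance of at least one false conclusion favouring the test device is up to 4.9% for independent or positively correlated tests, against 2.5% for RV1 alone. This rests on three things: no true effect on either endpoint, a lower limit taken from a two-sided 95% interval, and a correlation that the documents do not give. If one of the two effects is real, the joint rate is no higher than 2.5% with or without a gate. The change is worth making because it is cheap and settles the reading in advance. The trial's main conclusion does not depend on it.

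**What to change.** Add one sentence to section 10.4: the number of flow-stop episodes is tested for a formal conclusion only if superiority on RV1 has been shown under 10.3; otherwise the ratio and its 95% confidence interval are reported descriptively. State in the same sentence that the limit comes from a two-sided 95% interval.

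The RV1 test keeps its full level and the sample size does not change. With a single formal secondary test there is no further ordering to decide. The cost is that if RV1 fails, no formal flow-stop conclusion can be drawn, however strong that result looks. The estimate and interval would still be reported.
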